6.4. Appendix 4 Protocol Deviations

In general, the following list of major protocol deviations may have the potential to impact participants' rights, safety or well-being, or the integrity and/or result of the clinical study. Participants with major protocol deviations will be identified prior to database lock and the participants with major protocol deviations will be summarized by category.

- Developed withdrawal criteria but not withdrawn
- Entered but did not satisfy criteria
- Received a disallowed concomitant treatment ([Appendix 5](#))
- Received wrong treatment or incorrect dose
- Other

All major protocol deviations will be tabulated by coded term by study panel for the ITT. A listing of the major protocol deviations will be also presented.

A subset of major protocol deviations that may affect the assessment of efficacy (see list in [Attachment 2](#)) will be identified and finalized prior to database lock to define the Per-Protocol analysis set (see [Section 4](#)). The number and percentage of ITT participants who are included in the PP analysis set will be summarized by study panel, accompanied by number and percentage of ITT participants who are excluded from the PP analysis set with the incidence of the major protocol deviations.

6.5. Appendix 5 Prior and Concomitant Medications

Prior and Concomitant medications will be coded using the World Health Organization Drug Dictionary. Prior medications are defined as any therapy used before the day of first dose (partial or complete) of any study intervention. Concomitant medications are defined as any therapy used on or after the same day as the first dose of study interventions, including those that started before and continue on after the first dose of study interventions.

Summaries of concomitant medications will be presented by ATC class 2, level 4 and preferred term, study phase, study panel, and overall. The proportion of participants who receive each concomitant medication will be summarized as well as the proportion of participants who receive at least 1 concomitant medication.

Prior medications will be summarized by study panel and overall; as well ATC class 2, level 4 and preferred term.

6.6. Appendix 6 Medical History

A tabulation of the general medical history coded terms will be provided by body system class and by study panel and overall.

6.7. Appendix 7 Intervention Compliance

Compliance will be summarized descriptively on the Safety Set for each study treatment except NA.

Treatment compliance (%) is defined as follows:

For JNJ-3989: Total number of injections received / 12 * 100%

For JNJ-6379: Total medication intake / (4 * 7 * X) * 100%, where:

- Total medication intake = Total number of tablets dispensed – Total number of tablets returned.
- X = Number of weeks on 6379 (end date of JNJ-6379 – start date of JNJ-6379) for each participant. Note that the 250 mg daily dose of JNJ-6379 consists of 4 tablets (2 tablets of 100 mg strength and 2 tablets of 25 mg strength), so the denominator is 4*7*X.

For PegIFN- α 2a: Total number of injections received / Total number of injections supposed to receive * 100%

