1.2. Study Design

A target of 24 chronic HBV-infected male and female participants, 18-65 years (inclusive) of age

will be enrolled in Panels 1 and 2, approximately 12 participants in each panel. In Panel 3, a target of 4-6 chronic HBV-infected male and female participants will be enrolled.

- Panel 1 will consist of participants who are HBeAg positive and not currently treated.
- Panel 2 will consist of participants who are HBeAg negative and virologically suppressed by ETV, TD, or TAF treatment.
- Panel 3 will consist of participants who are HBeAg positive or negative and are either not currently treated or virologically suppressed by ETV or TD treatment.

The study will be conducted in 3 phases for all participants:

- A **screening phase** (4 to 6 weeks),
- An **open-label study intervention phase** (48 weeks),
- A **follow-up phase** (48 weeks). Note that the follow-up period will be extended up to an additional 24 weeks for participants who are receiving optional treatment with PegIFN- α 2a and who meet NA treatment completion criteria at the end of treatment with NA and PegIFN- α 2a to ensure all participants have at least one year of follow-up after NA treatment cessation.

The duration of individual participation will be up to 102 weeks for participants who stop NA treatment at the end of the open-label phase, or up to 126 weeks for participants who stop NA treatment during the follow-up phase.

Prior to Protocol Amendment 5, in Panels 1 and 2, participants were randomized in a 1:1 ratio within each panel to receive one of the following interventions (i.e., treatments) for 48 weeks:

- **Arm 1**, combination regimen JNJ-3989+JNJ-6379+NA:
 - 200 mg JNJ-3989 (SC injection Q4W, with the last injection at Week 44), and
 - 250 mg JNJ-6379 (tablets qd), and
 - NA: ETV, TD, or TAF (tablets qd)
- **Arm 2**, combination regimen JNJ-3989+NA:
 - 200 mg JNJ-3989 (SC injection Q4W, with the last injection at Week 44), and
 - NA: ETV, TD, or TAF (tablets qd).

As of Protocol Amendment 5, in Panels 1 and 2, participants who were previously randomized to Arm 1 had to stop JNJ-6379 treatment immediately but will still receive JNJ-3989 and NA – effectively joining Arm 2. New participants will enroll without randomization to Arm 2.

No participants were enrolled in Panel 3 before Protocol Amendment 5 was in effect. Therefore, all Panel 3 participants will enroll without randomization to receive the Arm 2 regimen.

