The number and percentage of participants who skipped any dose of JNJ-3989 or NA during the open-label phase, or any dose of PegIFN- α 2a, will be summarized separately by study panel. Additionally, the number and percentage of participants who missed 2 or more JNJ-3989 injections, or who missed more than 5 doses of NA within a four week period will be provided as well as the distribution of the total number of JNJ-3989 injections received.

Study intervention compliance will be summarized descriptively. See [Appendix 7](#) Intervention Compliance for further details.

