5.8. Interim Analyses

Two Interim Analyses (IA) may be performed: when all participants have completed Week 20 in the study intervention phase (or discontinued earlier) and when they have completed Week 72 (FU Week 24) in the follow-up phase (or discontinued earlier). These IAs will be performed by the sponsor to support interactions with health authorities, as well as to support internal decisions about additional studies and/or investigation of other combination regimens.

Both primary (when all participants have completed Week 48 or discontinued earlier) and interim analyses will be based on all data available at the predefined cut-off time points and may include data at later time points for those participants who have reached subsequent visits.

The final analysis will be performed when all participants have completed the last study visit (Follow-up Week 48) or discontinued earlier.

The overview of data domains and specific endpoints that will be provided for each analysis is presented in [Table 7](#).

Table 7: Overview of Times of Data Summaries and Analyses at Planned Interim, Primary and Final Analyses

	IA1 when all participants have completed Week 20	Primary Analysis when all participants have completed Week 48	IA2 when all participants have completed FU Week 24	Final Analysis when all participants have completed FU Week 48
DATA DOMAINS FOR ANALYSIS				
Subject Information				
Baseline & Demographic characteristics	X	X	X	X
Disposition and Study Populations	X	X	X	X
Extent of Exposure	X	X	X	X
Safety				
TEAEs, SAEs, AE of interest, fatal AEs, AEs causing treatment discontinuation	X	X	X	X
Laboratory Tests	X	X	X	X
ECG	X	X	X	X
Vital signs	X	X	X	X
Efficacy				
Primary efficacy endpoints		X	X	X
Secondary efficacy endpoints	X	X	X	X
Exploratory Endpoints	X	X	X	X
PK		X	X*	X*
Virologic breakthrough HBV	X	X	X	X
Flares: Viral, Biochemical, Clinical	X	X	X	X
Viral Genome Sequence Analysis		X	X	X

* If new data are available.

No DMC or Data Review Committee (DRC) is required for this study.

An Independent Flare Expert Panel (IFLEP) is appointed for this study to monitor ALT flares and make recommendations regarding flare management based on analysis of aggregate data. The IFLEP is composed of 3 independent medical experts with experience and expertise in hepatitis B and its treatment.

Further details on the IFLEP process will be provided in the IFLEP charter.

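### JNJ-3989 compliance is divided by a fixed 12 injections even when fewer were due, and the JNJ-6379 duration bracket omits the +1 and /7 that the SAP uses elsewhere

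*SAP*

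**What the plan says.** SAP Appendix 7 (section 6.7) defines percentage compliance for three drugs on the Safety set:

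- **JNJ-3989:** "For JNJ-3989: Total number of injections received / 12 * 100" percent. Nothing adjusts for a data cut-off or for stopping the drug. The regimen in SAP section 1.2 reads "200 mg JNJ-3989 (SC injection Q4W, with the last injection at Week 44), and" a nucleos(t)ide analog.
- **PegIFN-α2a:** "Total number of injections received / Total number of injections supposed to receive * 100" percent.
- **JNJ-6379:** tablets dispensed less tablets returned, divided by 4 × 7 × X, as a percentage. X is given as "Number of weeks on 6379 (end date of JNJ-6379", and the bracket closes after the start date is subtracted. The appendix explains the 4 as the daily tablet count.

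SAP section 5.6.1 writes the duration of JNJ-6379 exposure differently: last date minus first date, plus 1, all divided by 7.

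The same section states "Study intervention compliance will be summarized descriptively" and points to Appendix 7. Table 7 in SAP section 5.8 marks the Extent of Exposure domain for all four analyses, including the first interim. That interim is optional, is triggered once every participant has completed Week 20 or stopped before it, and, like the primary analysis, "may include data at later time points for those participants who have reached subsequent visits".

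**The concern.** A compliance percentage should compare what a participant took with what that participant was due to take. The constant 12 counts injections that were never due in two situations: when the data are cut before Week 44, and when JNJ-3989 is stopped early, including stops that Protocol section 7.1 requires. In both, a participant who missed nothing is reported as partly non-compliant. JNJ-3989 is the only one of the three drugs treated this way.

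The JNJ-6379 line has a different fault. Its label, its multiplier of 4 × 7 and its bracketed date arithmetic do not agree with each other or with section 5.6.1.

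What is at stake is a table that misstates adherence to the investigational drug. With about 12 participants per panel, one early stopper is enough to move a panel mean visibly.

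**Working it through.** **The plan's own figure.** Every 4 weeks from Day 1 (Week 0) to Week 44 gives 44/4 + 1 = 12 injections. The constant is correct for a full course.

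**Data cut before Week 44.** Injections due by Week t number t/4 + 1 for t a multiple of 4, to a maximum of 12. For a participant who has received every one:

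| Data end at | Due and received | Rule as written | Received/due |
|---|---|---|---|
| Week 20 | 6 | 6/12 = 50.0% | 100% |
| Week 24 | 7 | 58.3% | 100% |
| Week 28 | 8 | 66.7% | 100% |
| Week 32 | 9 | 75.0% | 100% |
| Week 36 | 10 | 83.3% | 100% |
| Week 40 | 11 | 91.7% | 100% |
| Week 44 or later | 12 | 100% | 100% |

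**Early stop.** A participant who received all k injections due before stopping reads k/12: 1/12 = 8.3%, 6/12 = 50.0%, 11/12 = 91.7%. Received/due gives 100% in each case. This effect does not disappear with follow-up, so it remains at the primary and final analyses.

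**Effect on a panel mean.** Take 12 participants, 11 with full courses and one who stopped after k injections with none missed. The reported mean is (11 × 100 + 100k/12)/12:

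- k = 1: (1100 + 8.3)/12 = 92.4%
- k = 6: (1100 + 50)/12 = 95.8%
- k = 11: (1100 + 91.7)/12 = 99.3%

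The documents give no actual stopping times, so this is a range rather than a forecast.

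**JNJ-6379.** Full intake over D days, counting both ends, is 4D tablets, and end date minus start date is D − 1. The three readings of X give:

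- Bracket taken literally, in days: 4D/[28(D − 1)]
- Difference divided by 7, no +1: 4D/[4(D − 1)] = D/(D − 1)
- As in section 5.6.1, (difference + 1)/7: 4D/4D

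| D (days) | Literal days | /7, no +1 | (difference + 1)/7 |
|---|---|---|---|
| 28 | 14.8% | 103.7% | 100% |
| 84 | 14.5% | 101.2% | 100% |
| 168 | 14.4% | 100.6% | 100% |
| 336 | 14.3% | 100.3% | 100% |

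The documents do not give the time any participant spent on JNJ-6379, so the durations are illustrative.

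**The case against.** The strongest defence is that received/12 is a legitimate measure of the share of the planned course. JNJ-3989 has a fixed 48-week duration, so a constant exists. PegIFN-α2a runs 12 or 24 weeks at the investigator's discretion, so its denominator has to vary. Under a due-based rule, a participant who stopped after one injection reads 100%, which says nothing about exposure. This stands as a reason to keep received/12 under an exposure label, but it does not make that figure compliance.

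Second, the context is reported elsewhere. Section 5.6.1 tabulates skipped JNJ-3989 doses, participants missing two or more injections, the distribution of injections received, and exposure duration. Section 5.2 gives discontinuations with reasons. A careful reader could therefore untangle the causes. That limits the harm but leaves the printed percentage wrong.

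Third, the JNJ-6379 line names X as weeks, and the factor 4 × 7 works only in weeks. A programmer would probably divide by 7. That stands: the likely residue is the missing +1, and the 14% to 15% reading requires coding the bracket literally.

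Four stronger readings are tempting, and the documents do not support them:

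- *That adherent participants generally read 50% at the Week 20 interim.* The trigger is the last participant reaching Week 20 and later data may be used, so earlier enrollees read 58% to 100%. The interim is also optional. The rationale for SAP Amendment 1 mentions a past interim analysis without saying which, so this use may already be over.
- *That a required stop gives 50%.* It does so only after exactly six injections.
- *That the 20% drop rate predicts the bias in the mean.* That rate is a sample-size allowance for incomplete data, not a JNJ-3989 stopping rate, and no typical number of injections is given. Even taking 20% at face value, 0.8 × 100 + 0.2 × (100k/12) runs from 81.7% to 98.3% for k = 1 to 11.
- *That compliance is used to interpret the Week 40 biopsies.* Nothing says so. The primary analysis uses all biopsy data, including those collected after treatment discontinuation.

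**Conclusion.** The point holds as a rule that is wrong as written, with small consequences. The JNJ-3989 percentage is correct only when all 12 injections have fallen due. For a participant who missed nothing it otherwise reads k/12: 8.3% to 91.7% after an early stop, and 50% when data end at Week 20. The JNJ-6379 bracket contradicts its own label and section 5.6.1. Sensibly coded without the +1, it overstates full intake by 3.7 percentage points at 28 days and 0.3 at 336 days; coded literally, it is wrong about sevenfold.

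The effect is confined to a descriptive table. The dosing items in Attachment 2 exclude participants from the per-protocol set for specific deviations, not for a compliance percentage, and no efficacy estimate uses it.

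The conclusion assumes the stated four-weekly schedule with its last injection at Week 44, and the usual meaning of compliance as doses taken out of doses due. The early-stop figures assume that every injection before the stop was received.

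**What to change.** Change two lines in SAP Appendix 7:

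- **JNJ-3989:** injections received, divided by injections scheduled from Day 1 up to the earliest of JNJ-3989 discontinuation, data cut-off and Week 44, × 100%. State how to count an injection scheduled on the discontinuation date, or one still inside the three-week catch-up allowance of Protocol section 6.4 at the cut-off.
- **JNJ-6379:** X = (end date − start date + 1)/7, matching section 5.6.1.

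If received/12 is still wanted, report it under Extent of Exposure, labelled *percent of planned course*.

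The cost is two formula lines and minor reprogramming. No data collection, treatment or other analysis changes.

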6.8. Appendix 8 Adverse Events of Special Interest

Adverse events of special interest are defined as follows:

AE Special Interest Category	Preferred Term
AST/ALT elevations	ALANINE AMINOTRANSFERASE ABNORMAL ALANINE AMINOTRANSFERASE INCREASED ASPARTATE AMINOTRANSFERASE ABNORMAL ASPARTATE AMINOTRANSFERASE INCREASED HEPATIC ENZYME ABNORMAL HEPATIC ENZYME INCREASED HEPATIC FUNCTION ABNORMAL HYPERTRANSAMINASAEMIA LIVER FUNCTION TEST ABNORMAL LIVER FUNCTION TEST INCREASED TRANSAMINASES ABNORMAL TRANSAMINASES INCREASED
Renal complications	ACUTE KIDNEY INJURY ANURIA NEPHROPATHY TOXIC OLIGURIA RENAL FAILURE RENAL IMPAIRMENT SUBACUTE KIDNEY INJURY BLOOD CREATININE ABNORMAL BLOOD CREATININE INCREASED CREATININE RENAL CLEARANCE ABNORMAL CREATININE RENAL CLEARANCE DECREASED CREATININE URINE ABNORMAL CREATININE URINE DECREASED CRYSTAL NEPHROPATHY GLOMERULAR FILTRATION RATE ABNORMAL GLOMERULAR FILTRATION RATE DECREASED NEPHRITIS PROTEINURIA RENAL FUNCTION TEST ABNORMAL RENAL TUBULAR DISORDER RENAL TUBULAR DYSFUNCTION RENAL TUBULAR INJURY RENAL TUBULAR NECROSIS URINE OUTPUT DECREASED NEPHROPATHY NEPHROPATHY TOXIC GLOMERULONEPHROPATHY NEPHROLITHIASIS
Hematologic Abnormalities	APLASTIC ANAEMIA AUTOIMMUNE APLASTIC ANAEMIA BICYTOPENIA

AE Special Interest Category	Preferred Term
	BONE MARROW FAILURE
	CYTOPENIA
	FEBRILE BONE MARROW APLASIA
	FULL BLOOD COUNT DECREASED
	GELATINOUS TRANSFORMATION OF THE BONE MARROW
	IMMUNE-MEDIATED PANCYTOPENIA
	PANCYTOPENIA
	PANMYELOPATHY
	ASPIRATION BONE MARROW ABNORMAL
	BIOPSY BONE MARROW ABNORMAL
	BLOOD DISORDER
	BONE MARROW DISORDER
	BONE MARROW INFILTRATION
	BONE MARROW MYELOGRAM ABNORMAL
	BONE MARROW NECROSIS
	HAEMATOTOXICITY
	MYELODYSPLASTIC SYNDROME
	MYELODYSPLASTIC SYNDROME TRANSFORMATION
	MYELOFIBROSIS
	MYELOID METAPLASIA
	PLASMA BLAST COUNT DECREASED
	SCAN BONE MARROW ABNORMAL
	APLASIA PURE RED CELL
	APLASTIC ANAEMIA
	ERYTHROBLAST COUNT DECREASED
	ERYTHROID MATURATION ARREST
	ERYTHROPOENIA
	HYPOPLASTIC ANAEMIA
	MICROCYTIC ANAEMIA
	PROERYTHROBLAST COUNT DECREASED
	RED BLOOD CELL COUNT DECREASED
	RETICULOCYTE COUNT DECREASED
	RETICULOCYTOPENIA
	ANAEMIA
	ERYTHROBLAST COUNT ABNORMAL
	ERYTHROPOESIS ABNORMAL
	HAEMATOCRIT ABNORMAL
	HAEMATOCRIT DECREASED
	HAEMOGLOBIN ABNORMAL
	HAEMOGLOBIN DECREASED
	LEUKOERYTHROBLASTIC ANAEMIA
	NORMOCHROMIC ANAEMIA
	NORMOCHROMIC NORMOCYTIC ANAEMIA
	NORMOCYTIC ANAEMIA
	PROERYTHROBLAST COUNT ABNORMAL
	RED BLOOD CELL COUNT ABNORMAL
	RETICULOCYTE COUNT ABNORMAL

AE Special Interest Category	Preferred Term
	RETICULOCYTE PERCENTAGE DECREASED
	AGRANULOCYTOSIS
	BAND NEUTROPHIL COUNT DECREASED
	BAND NEUTROPHIL PERCENTAGE DECREASED
	BASOPHIL COUNT DECREASED
	BASOPHILONIA
	B-LYMPHOCYTE COUNT DECREASED
	CYCLIC NEUTROPENIA
	EOSINOPENIA
	EOSINOPHIL COUNT DECREASED
	FEBRILE NEUTROPENIA
	GRANULOCYTE COUNT DECREASED
	GRANULOCYTES MATURATION ARREST
	GRANULOCYTOPENIA
	IDIOPATHIC NEUTROPENIA
	LEUKOPENIA
	LYMPHOCYTE COUNT DECREASED
	LYMPHOPENIA
	METAMYELOCYTE COUNT DECREASED
	MONOBLAST COUNT DECREASED
	MONOCYTE COUNT DECREASED
	MONOCYTOPENIA
	MYELOBLAST COUNT DECREASED
	MYELOCYTE COUNT DECREASED
	NEUTROPENIA
	NEUTROPENIC INFECTION
	NEUTROPENIC SEPSIS
	NEUTROPHIL COUNT DECREASED
	PROMYELOCYTE COUNT DECREASED
	PURE WHITE CELL APLASIA
	T-LYMPHOCYTE COUNT DECREASED
	WHITE BLOOD CELL COUNT DECREASED
	BASOPHIL COUNT ABNORMAL
	BASOPHIL PERCENTAGE DECREASED
	B-LYMPHOCYTE ABNORMALITIES
	B-LYMPHOCYTE COUNT ABNORMAL
	DIFFERENTIAL WHITE BLOOD CELL COUNT ABNORMAL
	EOSINOPHIL COUNT ABNORMAL
	EOSINOPHIL PERCENTAGE DECREASED
	FULL BLOOD COUNT ABNORMAL
	GRANULOCYTES ABNORMAL
	LEUKOPENIA NEONATAL
	LYMPHOCYTE COUNT ABNORMAL
	LYMPHOCYTE PERCENTAGE ABNORMAL
	LYMPHOCYTE PERCENTAGE DECREASED
	MONOCYTE COUNT ABNORMAL
	MONOCYTE PERCENTAGE DECREASED

AE Special Interest Category	Preferred Term
	MONONUCLEAR CELL COUNT DECREASED
	MYELOBLAST PERCENTAGE DECREASED
	MYELOCYTE PERCENTAGE DECREASED
	MYELOID MATURATION ARREST
	NEUTROPHIL COUNT ABNORMAL
	NEUTROPHIL PERCENTAGE DECREASED
	PLASMA CELL DISORDER
	PLASMA CELLS ABSENT
	WHITE BLOOD CELL ANALYSIS ABNORMAL
	WHITE BLOOD CELL COUNT ABNORMAL
	WHITE BLOOD CELL DISORDER
	ACQUIRED AMEGAKARYOCYTIC THROMBOCYTOPENIA
	MEGAKARYOCYTES DECREASED
	PLATELET COUNT DECREASED
	PLATELET MATURATION ARREST
	PLATELET PRODUCTION DECREASED
	PLATELET TOXICITY
	THROMBOCYTOPENIA
	MEGAKARYOCYTES ABNORMAL
	PLATELET COUNT ABNORMAL
	PLATELET DISORDER
	PLATELETCRIT ABNORMAL
	PLATELETCRIT DECREASED
Cholesterol Increase	BLOOD CHOLESTEROL ABNORMAL
	BLOOD CHOLESTEROL ESTERASE INCREASED
	BLOOD CHOLESTEROL INCREASED
	DYSLIPIDAEMIA
	HIGH DENSITY LIPOPROTEIN ABNORMAL
	HIGH DENSITY LIPOPROTEIN DECREASED
	HIGH DENSITY LIPOPROTEIN INCREASED
	HYPERCHOLESTEROLAEMIA
	HYPERLIPIDAEMIA
	HYPOL HDL CHOLESTEROLAEMIA
	INTERMEDIATE DENSITY LIPOPROTEIN DECREASED
	INTERMEDIATE DENSITY LIPOPROTEIN INCREASED
	LDL/HDL RATIO DECREASED
	LDL/HDL RATIO INCREASED
	LIPID METABOLISM DISORDER
	LIPIDS ABNORMAL
	LIPIDS INCREASED
	LIPOPROTEIN ABNORMAL
	LIPOPROTEIN INCREASED
	LOW DENSITY LIPOPROTEIN ABNORMAL
	LOW DENSITY LIPOPROTEIN DECREASED
	LOW DENSITY LIPOPROTEIN INCREASED
	NON-HIGH-DENSITY LIPOPROTEIN CHOLESTEROL DECREASED
	NON-HIGH-DENSITY LIPOPROTEIN CHOLESTEROL INCREASED

AE Special Interest Category	Preferred Term
	PRIMARY HYPERCHOLESTEROLAEMIA
	REMNANT HYPERLIPIDAEMIA
	REMNANT-LIKE LIPOPROTEIN PARTICLES INCREASED
	TOTAL CHOLESTEROL/HDL RATIO ABNORMAL
	TOTAL CHOLESTEROL/HDL RATIO DECREASED
	TOTAL CHOLESTEROL/HDL RATIO INCREASED
	VERY LOW DENSITY LIPOPROTEIN ABNORMAL
	VERY LOW DENSITY LIPOPROTEIN DECREASED
	VERY LOW DENSITY LIPOPROTEIN INCREASED

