### **2.3.2. Risks for Study Participation**

#### **2.3.2.1. Known Risks**

No known risks associated with JNJ-3989 or JNJ-6379 have been identified from clinical observations so far in the Phase 1 and 2 studies. Injection site reactions were identified as adverse drug reactions for JNJ-3989.

The side effect profile of PegIFN- $\alpha$ 2a is well established and includes, but is not limited to, neuropsychiatric, autoimmune, ischemic, ophthalmologic, hematological, and infectious disorders. Exacerbations of hepatitis during hepatitis B therapy are common and characterized by transient and potentially severe increases in serum ALT. Marked increases in ALT were sometimes accompanied by bilirubin elevation and other liver test abnormalities. In many, but not all cases, these disorders resolve after stopping PegIFN- $\alpha$ 2a therapy. For a full list of known risks for PegIFN- $\alpha$ 2a, refer to the respective prescribing information.

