### **8.5.6. Adverse Events of Special Interest**

Events of Special Interest are significant AEs that are judged to be of special interest because of clinical importance, known class effects or based on nonclinical signals. Events of Special Interest that will be carefully monitored during the study include ISRs, ALT/AST elevations, renal complications, hematological abnormalities, and events related to cholesterol increase (Section 8.4.4, Clinical Safety Laboratory Assessments). In addition, the following toxicities will also be carefully monitored: rash and acute systemic allergic reactions.

For participants reporting ALT/AST elevations, rash, ISRs, acute systemic allergic reactions, renal complications, and hematological abnormalities as specified in the DAIDS Toxicity Grading Scale (see Section 10.9, Appendix 9, DAIDS Table), the following should be done.

Note: renal complications and cholesterol increase are AESIs specific for JNJ-6379, which was part of the study intervention up to Protocol Amendment 4 and has been removed with the implementation of Protocol Amendment 5. Because participants who were enrolled before Protocol Amendment 5 was in effect, also received JNJ-6379 as part of their study intervention, the AESIs have not been revised with the removal of JNJ-6379. For all participants having received at least one dose of JNJ-6379, renal safety monitoring will be continued.

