### 8.5.6.1. Injection Site Reactions

At the time points specified in the [Schedule of Activities](#) or at an unscheduled visit if needed, an evaluation of the injection site will be performed based on participant's description and/or physical examination. Evaluations will be recorded in the source documents and will include at a minimum the time of occurrence, time of resolution and a description of the abnormality including its maximal diameter. For each ISR, information on pain, erythema, induration and pruritus should be obtained as specified in the DAIDS scale (see Section [10.9](#), Appendix 9, DAIDS Table).

All ISRs (including ISRs below grade 1) should be recorded in the special events section of the CRF.

Digital pictures will be taken when considered appropriate; all efforts should be made to collect images in case of grade 3 and 4 ISRs. Digital pictures will only be taken and collected from participants who consent separately to this component of the study. If digital pictures are required, they should be de-identified and provided to the sponsor.

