#### **9.4.2. Safety Analyses**

All safety analyses will be made on the Safety Population (Section 9.3).

Safety will be evaluated by means of descriptive summaries of AEs including AEs of special interest to any of the study interventions, clinical laboratory tests, ECGs, vital signs, and physical examinations. The safety analysis will be done by study phase. Results will be presented in tabular format and/or graphically over time, as appropriate.

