## **SEVERITY CRITERIA**

An assessment of severity grade will be made by the investigator using the general categorical descriptors outlined in the DAIDS Toxicity Grading Scale (see Section 10.9, Appendix 9, DAIDS Table).

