5.6.2. Adverse Events

The verbatim terms used in the CRF by investigators to identify adverse events will be coded using the Medical Dictionary for Regulatory Activities (MedDRA). Any AE occurring at or after the initial administration of study intervention is considered to be treatment emergent. If the event occurs on the day of the initial administration of study intervention, and either event time or time of administration are missing, then the event will be assumed to be treatment emergent. If the event date is recorded as partial or completely missing, then the event will be considered to be treatment emergent unless it is known to be prior to the first administration of study intervention based on partial onset date or resolution date. All reported treatment-emergent adverse events will be included in the analysis. For each adverse event, the number and percentage of participants who experience at least 1 occurrence of the given event will be summarized.

Summary tables will be provided for treatment-emergent adverse events:

- AEs
- Serious AEs (SAEs)

- AEs leading to discontinuation of each study agent within a study intervention including NA
- AEs by NCI-CTAE toxicity grade
- AEs by relationship to each study agent within a study intervention including NA

In addition to the summary tables, listings will be provided for participants who:

- Had SAEs
- Had AEs leading to discontinuation of each study agent within a study intervention including NA

Incidence of other treatment-emergent adverse events of special interest listed in [Appendix 8](#) will be summarized.

A listing of participants who died will be provided.

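### SAP Appendix 8 has no injection site reaction category although the protocol names these as events of special interest; two minor adverse-event mismatches sit beside it

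*SAP*

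**What the plan says.** **Protocol.** Section 8.5.6 says the events of special interest to be monitored "include ISRs, ALT/AST elevations, renal complications, hematological abnormalities, and events related to cholesterol increase"; section 2.3.3 gives the same list. Section 2.3.2.1 adds: "Injection site reactions were identified as adverse drug reactions for JNJ-3989". Section 8.5.2 makes ISRs the solicited adverse events, and section 8.5.6.1 requires: "All ISRs (including ISRs below grade 1) should be recorded in the special events section of the CRF". On analysis, section 9.4.2 commits to the following: "Safety will be evaluated by means of descriptive summaries of AEs including AEs of special interest to any of the study interventions". For severity, Appendix 4 tells the investigator to use the general descriptors "outlined in the DAIDS Toxicity Grading Scale", and Appendix 9 reproduces that scale as the one for AE reporting.

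**SAP.** Section 5.6.2 plans an incidence summary of the AESIs listed in Appendix 8. That appendix defines four categories by preferred term: AST/ALT elevations, renal complications, hematologic abnormalities and Cholesterol Increase. The last contains "LOW DENSITY LIPOPROTEIN DECREASED" and "INTERMEDIATE DENSITY LIPOPROTEIN DECREASED", among others. Section 5.6.2 also lists a table of "AEs by NCI-CTAE toxicity grade". Section 5.6.3.1 and Appendix 9 grade laboratory values on DAIDS. Appendix 2 states that nothing departs from the protocol-planned analyses.

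**The concern.** Safety is a secondary objective, and SAP Table 7 schedules AEs of interest at all four planned analyses. Appendix 8 decides which events get that summary.

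The protocol's note in 8.5.6 says the renal and cholesterol AESIs are specific to JNJ-6379, which was withdrawn at Amendment 5, and that the list was deliberately left unrevised because some participants had already received that drug. The SAP therefore keeps the two groups tied to the withdrawn drug and lacks the one tied to JNJ-3989, which every participant receives, up to 12 injections each (SAP Appendix 7). The SAP version history records no decision to leave ISRs out, so this looks like an oversight.

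The other two items are smaller. A category named for an increase should not count AEs coded as decreases, and a severity table should name the scale on which the events were graded.

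**Working it through.** The plan states no figure to reproduce. The check is a side-by-side reading plus a count of terms.

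**1. AESI groups**

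| Protocol 8.5.6 | SAP Appendix 8 |
|---|---|
| Injection site reactions | none |
| ALT/AST elevations | present |
| Renal complications | present |
| Hematological abnormalities | present |
| Cholesterol increase | present |

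Five groups against four; 5 − 4 = 1 missing, the ISRs. No other SAP section plans an ISR summary.

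**2. Where ISRs could still appear.** SAP 5.6.2 includes all reported treatment-emergent AEs, with number and percentage per event. An ISR entered as an AE is therefore tabulated under its own preferred term. An ISR recorded only in the special events section of the CRF might not be. Those below grade 1 are the likeliest: in the DAIDS table, grade 1 injection site erythema in adults starts at 2.5 cm, so smaller reactions can be recorded without reaching a grade. The CRF and its database mapping are not in the documents, so this stays a possibility.

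**3. Terms under Cholesterol Increase**

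- Ending in INCREASED: 12
- Ending in ABNORMAL: 7
- Ending in DECREASED: 7 (HDL, IDL, LDL, VLDL, non-HDL cholesterol, LDL/HDL ratio, total cholesterol/HDL ratio)
- Other: 7 (dyslipidaemia, hypercholesterolaemia, hyperlipidaemia, low HDL cholesterol, lipid metabolism disorder, primary hypercholesterolaemia, remnant hyperlipidaemia)
- Total: 12 + 7 + 7 + 7 = 33

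Low HDL can fairly be read as part of a dyslipidaemia, so HDL decreased is set aside: 7 − 1 = 6 terms run against the category name, and 6/33 = 18%. Counting HDL decreased and the low-HDL term as well gives 8/33 = 24%.

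**4. Size of one wrongly counted participant.** In Panels 1 and 2 at target, 1/24 = 4.2 percentage points. Adding the 4 Panel 3 participants mentioned in the SAP introduction, 1/28 = 3.6 points. This applies only if such an AE is reported; the documents give no rate.

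**5. Severity scale.** The protocol grades AEs on DAIDS (Appendices 4 and 9). SAP 5.6.2 names NCI-CTAE, apparently a misspelling of CTCAE, which the SAP abbreviation list defines. The SAP contains neither CTCAE criteria nor a re-grading step.

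**The case against.** The strongest reply is that little information is lost, and much of it stands.

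- **ISRs.** A reader might infer that ISRs get no summary at all. The documents do not support that: ISRs are solicited AEs, and 5.6.2 tabulates every reported treatment-emergent AE. Nor does the protocol say that entries in the special events section stay out of the AE dataset. What remains is the missing grouped summary of a protocol-named AESI, plus uncertainty about reactions recorded only in that section.
- **Cholesterol.** A reader might infer that any participant whose LDL falls is counted as a cholesterol increase. That is too strong. Appendix 8 lists AE preferred terms, not laboratory values, so a fall counts only if it is reported as an AE and coded to one of these terms. Protocol Appendix 9 notes that laboratory abnormalities are not necessarily AEs, and its table grades only high fasting cholesterol and high fasting LDL. Laboratory cholesterol is analysed separately, with the worst grade derived by direction (SAP Table 5 and 5.6.3.1). The list may also be a deliberately broad search, since it holds seven non-directional ABNORMAL terms. Breadth does not explain placing explicit decreases under the name of an increase.
- **Severity.** A reader might infer that the table would report grades on a scale nobody used. Because only DAIDS grades are recorded and no re-grading is planned, a mislabelled table is the likelier outcome.

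**Conclusion.** The point holds, and the ISR omission carries most of its weight. SAP Appendix 8 leaves out one of five protocol-named AESI groups, the one identified as an adverse drug reaction to the only investigational drug given to everyone, and SAP Appendix 2 does not declare it. The loss is a dedicated summary, and possibly the ISRs held only in the special events section; it is not all ISR reporting.

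The lipid terms are minor. Six of 33 point the wrong way and can only inflate the category, by about 4 percentage points for each participant so counted; the number of such participants is unknown and may be zero. The severity label is also minor and probably editorial.

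None of this touches the primary endpoint. The conclusion rests on the SAP text alone. It assumes that no separate programming document already adds an ISR table, and it makes no assumption about how the CRF maps special events into the AE dataset.

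**What to change.** 1. **Appendix 8:** add an injection site reactions category covering the injection-site preferred terms, and state that its summary also draws on the special events section of the CRF, including reactions below grade 1. A split between JNJ-3989 and PegIFN-α2a is optional.
2. **Appendix 8, Cholesterol Increase:** remove the six decrease terms (LDL, IDL, VLDL, non-HDL cholesterol, LDL/HDL ratio, total cholesterol/HDL ratio) or report them on a separate line. The non-directional ABNORMAL terms would remain, so a footnote should say that the category is not purely directional.
3. **Section 5.6.2:** replace NCI-CTAE with the DAIDS grade recorded by the investigator.
4. If any of these departures is intended, declare and justify it in Appendix 2 instead.

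The same edit can correct the SAP's cross-reference for the DAIDS table, which cites protocol Appendix 8; the table is in protocol Appendix 9.

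The cost is an edit to one appendix and one line of 5.6.2, plus one extra table from data the protocol already collects.
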